Sample Size Considerations. As described in the original application (i.e., R01HD091155-A1), we conducted a conventional power analysis using G*Power (Version 3.1.9.5) and estimated the appropriate sample size for detecting differences in follow-up SDMT scores, controlling for baseline score (Specific Aim 1). Using G*Power, this was accomplished using the 'F test' selection within the 'Test' family menu, and the Statistical Test of 'ANCOVA: Fixed effects, main effects and interactions'. The effect size ($\eta_p^2=0.11$) for the power analysis was computed from our pilot RCT¹² of TMWX training compared with a waitlist control condition on SDMT scores in persons with MS who had mild ambulatory disability, but not CPS impairment. That effect size was smaller than the effect sizes for thalamocortical RSFC outcomes, and thus was included in the main power analysis as a conservative approach. The power analysis included standard assumptions of alpha (0.05) and beta (0.80). The power analysis indicated that the minimal total sample size for testing group differences on follow-up SDMT scores, controlling for baseline scores should be 66 participants (33 per group). This supports our goal of recruiting 88 participants (44 per condition) as yielding adequate power, based on retention of 75% of the enrolled participants. The current application proposes a change of grantee organization whereby the final 72 participants will be enrolled at KF. We will explore the possible influence of study site on the outcomes in *post-hoc* sensitivity analyses. We expect that the effects of study site are likely negligible given the constants of the study team and standardized manuals of operating procedures that guide all study aspects.

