Statistical Analysis. The data analyses will be overseen by [name] and follow intent-to-treat principles (i.e., include all persons regardless of dropout). In the case of a drop-out, missing data will be imputed by carrying the last observed value forward. We further will perform exploratory data analyses only in those who completed follow-up testing (i.e., completer's or per protocol analysis) and in those who demonstrated good adherence (i.e., attended at least 83% of sessions) and compliance. The analytic plan will account for several potential confounders of the effects of progressive TMWX training on the outcome measures. These include MS duration, BMI, age, sex, cognitive reserve, T2-lesion volume, and relapse rate. If these variables differ between groups, they will be included as additional covariates in the following analyses.

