improvement at the brain-systems level in the general population²⁸. As pre-conditions of the mediation analysis, we will first perform correlations among group (i.e., exercise or control), change in SDMT scores, and change in RSFC between the thalamus and right MFG and ACC, respectively, using Spearman's rho rank-order correlations (ρ)⁹¹ to test if those outcomes are interrelated. Consistent with our pilot work¹², we expect that TMWX training will be associated with improvements in CPS and increases in thalamocortical RSFC. Moreover, we expect that improvements in CPS will be associated with increases in thalamocortical RSFC. Then, to establish mediation, we will perform hierarchical linear regression models for evaluating each of the two mediators (i.e., changes in RSFC between thalamus/right MFG, and RSFC between thalamus/ACC, respectively), separately. This will involve regressing change in SDMT score on group in Step 1 and then adding change in the mediator in Step 2. In order to establish mediation, if the pre-conditions are met, group must influence change in SDMT in Step 1, and the mediator must influence change in SDMT score in Step 2 of the regression as well as attenuate the effect of group on SDMT scores (i.e., the effect of group on SDMT should be reduced and become non-significant between Step 1 and Step 2)⁸⁹. As such, we expect significant effects of group on change in CPS, and that the effect of group (i.e., exercise or control) on change in CPS will be attenuated, but not reach zero, when accounting for the effects of changes in thalamocortical RSFC. In other words, we expect that changes in thalamocortical RSFC will be partial mediators of the effects of TMWX training on CPS in persons with MS with impaired CPS.

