Analysis by Race/Gender. We anticipate that 70% of participants will be female and 70% will be Caucasian. We will test the effects of gender and race on the intervention effects, and if there are interactions, we will separately analyze by gender/race to explore the specific effects of the variables on the outcomes. We do recognize that we will not likely enroll sufficient numbers of male participants or participants of Hispanic ethnicity and or other races to make meaningful comparisons.

Treatment of Missing Data. We conservatively plan for approximately 25% attrition based on a previous large RCT of 6-months (i.e., a longer intervention period than the proposed study) of multimodal exercise training versus a stretching-and-toning control condition on mobility outcomes in persons with moderate-to-severe MS-related ambulatory disability in our laboratory⁵⁶. In that study, the adherence rates for both the exercise and stretching-and-toning conditions were upwards of 75%, despite a significant barrier to participation being the inclusion of persons with substantial ambulatory disability. Of note, those adherence rates are *lower* than the overall average adherence rates for exercise trials involving persons with MS, based on a recent systematic review (i.e., upwards of 84% for both exercise and control conditions)⁵⁷. Nevertheless we have plans for

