exploring and examining the impact of such losses, as we could have upwards of 25% drop-out, given that this sample includes persons with objective CPS impairment. Initially, analyses will be done on the data set using last observation carried forward and then on the actual data collected (case-wise deletion), followed by multiple imputation for missing data. All analyses at present are planned using SPSS software (version 25 or higher), although as new options continue to evolve with SAS or R; these will be considered if there are new tools for imputation that will help understand the impact of missing data. We believe that these imputations should involve fewer than 15% of the participants, which then should have minimal impact on the analyses. However, it is important to assess this from a best case and worst case scenario and if the results are consistent, then we can be more confident of our findings. If these analyses yield differing results – more exploratory analyses are required to understand if the differences in the outcomes are coming from the control condition or the intervention condition. If the control condition, the implications can be examined in one way and if the intervention condition, it is likely to add cautionary notes to the findings.

Interim and Final Analysis. We do not plan any interim efficacy or futility analyses. The study team will work together for publications on the protocol, fidelity monitoring plan, as well as the primary study outcomes.

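### Carry-forward puts participants without follow-up at zero change on both SDMT and RSFC, which inflates the Aim 2 mediator test, and no rule says which missing-data analysis decides mediation

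*Combined protocol and SAP*

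**What the plan says.** The SAP (Statistical Design and Power), under Statistical Analysis, keeps all participants in the analysis whether or not they drop out, and adds: "In the case of a drop-out, missing data will be imputed by carrying the last observed value forward". Protocol section 5.3 has the same rule. Protocol sections 1 and 5.2.2 place outcome assessment at baseline and after the 12-week period only.

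The SAP's Specific Aim 2 text uses change scores for outcome and mediator: "This will involve regressing change in SDMT score on group in Step 1 and then adding change in the mediator in Step 2". Mediation is established if all of these hold:
- group, SDMT change and RSFC change are interrelated (Spearman pre-conditions);
- group affects SDMT change in Step 1;
- the mediator affects SDMT change in Step 2;
- the group effect shrinks and loses significance in Step 2.

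The rule is applied to two mediators separately, thalamus/right MFG and thalamus/ACC.

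Under Treatment of Missing Data the SAP says "We conservatively plan for approximately 25% attrition", and later that "these imputations should involve fewer than 15% of the participants". That section runs carry-forward first, then case-wise deletion, then multiple imputation. If the results differ, it calls for more exploratory work. The completer analysis (Statistical Analysis; section 5.3) is labelled exploratory. None of these provisions names Aim 2.

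**The concern.** With only two assessments, the last observed value of someone lost before follow-up is the baseline value. That person's change is exactly zero on SDMT and exactly zero on RSFC. The pair is produced by the imputation rule and says nothing about whether connectivity and processing speed move together. If the observed participants lie, on average, above zero on both axes, a cluster at the origin tilts the fitted slope upward. The mediator term and the SDMT-RSFC Spearman pre-condition then become easier to meet as dropout grows.

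This is separate from what carry-forward does to the Aim 1 group comparisons. Here it affects the mediator-outcome path, on which the mechanism claim in Hypothesis 2 rests.

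**Working it through.** **1. The plan's own figure.** The SAP gives "standard assumptions of alpha (0.05) and beta (0.80" (the second value is the power) and "The effect size ($\eta_p^2=0.11$) for the power analysis was computed from our pilot RCT". Then f² = 0.11/0.89 = 0.1236 and f = 0.352. With noncentrality f²N on 1 and N − 3 df, power is 0.797 at N = 65 and 0.803 at N = 66. This reproduces "should be 66 participants (33 per group"). Enrolment is 66/0.75 = 88, which matches "our goal of recruiting 88 participants (44 per condition) as yielding adequate power, based on retention of 75% of the enrolled participants". The documents give no power or error figure for Aim 2.

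**2. How many pairs.** 25% of 88 is 22 participants, 11 per arm.

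**3. Induced association.** Let d be the dropout fraction, and μY and μM the mean SDMT and RSFC changes in an arm, in SD units. With no true link within the arm, and dropouts set to (0,0):
- covariance = (1−d)μYμM − (1−d)²μYμM = d(1−d)μYμM
- variance of each change = (1−d) + d(1−d)μ²

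Step 2 adjusts for group, so these are averaged over the two arms.

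Assumptions not in the documents: change SD 1, dropout random and equal by arm, group effects of 0.70 SD on SDMT and 0.84 SD on RSFC. The first is 2f = 0.70. The second is 2√(0.15/0.85) = 0.84 for an assumed η² of 0.15; the SAP says only that the RSFC effects exceeded 0.11.

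*No common gain, d = 0.25.* Covariance = 0.1875 × (0.70 × 0.84)/2 = 0.0551. Variances are 0.75 + 0.1875 × 0.49/2 = 0.796 and 0.75 + 0.1875 × 0.7056/2 = 0.816. Partial r = 0.0551/√(0.796 × 0.816) = 0.068.

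*SDMT gain of 0.5 SD in both arms.* Covariance = 0.1875 × (1.20 × 0.84)/2 = 0.0945. The SDMT variance is 0.75 + 0.1875 × (1.44 + 0.25)/2 = 0.908. Partial r = 0.0945/√(0.908 × 0.816) = 0.110.

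Some common SDMT gain is plausible. Section 5.2.3.1 selects on a low Visit 1 SDMT, and no second baseline SDMT is listed, so observed participants can regress upward while carried-forward ones cannot. Its size is an assumption.

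**4. Standard error.** With no mean change in either variable the expected r is 0. But r then comes from (1−d)N real pairs and is tested as if from N. The two-sided error rate is 2[1 − Φ(1.96√(1−d))]: 9.0% at d = 0.25 and 7.1% at d = 0.15, instead of 5%.

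**5. Simulated error rates**, no true link, 3,000 to 6,000 trials per scenario. The Step 2 column counts a positive mediator term with p < 0.05, so its nominal rate is 2.5%.

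| Dropout | SDMT gain, both arms | RSFC shift, both arms | Step 2 term | Full Aim 2 rule |
|---|---|---|---|---|
| 25% | 0 | 0 | about 11% | about 3% |
| 25% | 0.5 SD | 0 | about 20% | about 6% |
| 25% | 0.5 SD | +0.3 SD | about 35% | about 10% |
| 25% | 0.5 SD | −0.3 SD | about 9% | about 3% |
| 15% | 0 to 0.5 SD | 0 | about 7–10% | about 1.5–3.5% |
| Observed pairs only | – | – | about 2.5% | about 0.7% |

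**6. A second set of means** (both changes 1 SD under exercise, 0 in control, 25% dropout) shows the same pattern. The mean partial r is 0.11, and the two-sided Step 2 rate is 20.4% against 5.0% in observed pairs. The SDMT-RSFC Spearman pre-condition is met in 63.5% against 38%. From Step 1 to Step 2 the group coefficient falls from 0.749 to 0.661 under carry-forward; in observed pairs it stays put (0.995 and 0.996).

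**The case against.** The strongest reply is that the plan already contains the remedy. Case-wise deletion and multiple imputation are listed in terms as general as the carry-forward rule, so on the same reading they reach Aim 2, and the case-wise run would expose the artefact. This stands in part: a reader who infers that the plan has no other missing-data analysis would be wrong. What it lacks is precedence. Carry-forward comes first, completers are exploratory, and nothing says which result settles mediation when they differ.

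Second, the Step 2 term is one element of a longer rule. A reader might take its error rate as the rate of false mediation claims. The documents do not support that, because the other conditions hold the full-rule rate to about 3% to 6% at 25% dropout without RSFC drift.

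Third, larger figures can be produced. Rates of about 45% for the term and 14% to 15% for the rule need a 0.8 SD SDMT gain and a 0.3 SD RSFC rise in both arms, controls included. Nothing in the documents supports that RSFC rise, and alternate forms (section 5.2.1) are meant to limit practice gains, though they do not prevent regression to the mean. The drift could also run the other way. With RSFC down 0.84 SD in both arms, so that controls decline and exercise holds steady, the rates were 1.3% and 0.3%, below those in observed pairs (2.8% and 1.0%).

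Fourth, not every dropout sits at (0,0). Follow-up SDMT is at Visit 1 and the MRI at Visit 2, so someone lost between them has an observed SDMT change. Nor does carry-forward always create a systematic association; that needs non-zero means on both variables within an arm. Both limits stand.

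**Conclusion.** The point holds in a bounded form. Carry-forward biases the mediator-outcome path toward Hypothesis 2 in the situation the plan itself expects, with both measures rising under exercise. The complete mediation rule is then falsely met roughly four to nine times as often as in observed pairs (3/0.7 to 6/0.7), but the absolute rate stays near 5% unless RSFC also rises in both arms. If dropout is nearer the SAP's more hopeful 15%, the inflation is smaller but still present.

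The direction follows from the documents. The sizes rest on the assumed mean changes, unit SDs and random, equal dropout. The Aim 1 treatment comparisons are not touched by this point, so it is a should-fix. A reader might infer that it undermines the trial's primary result; the documents do not support that.

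**What to change.** Add to Specific Aim 2 of the SAP:

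> Mediation is judged on participants with both follow-up SDMT and follow-up RSFC observed, with the multiple imputation described under Treatment of Missing Data (SDMT and RSFC imputed jointly, including group and both baselines) as sensitivity. Carried-forward values are not used to establish mediation.

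Both methods are already in the plan, and no data collection changes. At 25% attrition the nominal N for Aim 2 falls from 88 to about 66, and Aim 2 no longer covers everyone randomised, which should be stated as a departure from the general intent-to-treat rule. Little is lost on the mediator-outcome link, because the carried-forward pairs hold no information about it. Observed pairs may still be selective if dropout depends on the outcomes; the imputation analysis is there to probe that.

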STUDY PROTOCOL AND STATISTICAL ANALYSIS PLAN

Study Title: Exercise Training Effects on Cognition and Brain Function in Multiple Sclerosis: A Systematically-Developed Randomized Controlled Trial

NCT Number: NCT03677440

Date: 5/21/2020

Study Protocol

1. Abstract

Slowed cognitive processing speed (CPS) is a common and debilitating consequence of multiple sclerosis (MS) that is notoriously difficult to treat. As such, we undertook a systematic line of research that indicated that supervised, progressive treadmill walking exercise (TMWX) training might improve CPS and brain functioning among fully-ambulatory persons with MS. The current study will be the first adequately-powered, single-blind randomized controlled trial (RCT) that examines the efficacy of 12-weeks of TMWX training compared with an active control condition on CPS, thalamocortical brain connectivity (based on resting-state fMRI), and exploratory functional outcomes in 88 fully-ambulatory persons with MS who present with slowed CPS. 65 of those persons will be recruited at Kessler Foundation. The intervention condition involves supervised, progressive TMWX training 3 times/week over 12-weeks; this initially involves 15-minutes of light-to-moderate intensity TMWX that progresses up to 40-minutes of vigorous intensity TMWX. The active control condition involves supervised, minimal intensity, stretching-and-resistance exercise that will be delivered on the same frequency as the intervention condition. The primary study outcomes involve Symbol Digit Modalities Test performance (i.e., CPS) and fMRI-based measures of thalamocortical resting-state functional connectivity. Exploratory study outcomes involve measures of community participation, activities of daily living, quality of life, and functional mobility. All study outcomes will be administered before and after the 12-week study period by treatment-blinded assessors. If successful, the current study will provide the first Class I evidence for the effects of TMWX training as an approach for improving CPS and its neural correlate, and possibly mitigating the impact of slowed CPS on functional outcomes in MS.

2. Study Objectives

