The proposed research represents the first opportunity to investigate the efficacy, possible mechanism, and functional impact of treadmill walking exercise training on CPS and thalamocortical RSFC in fully-ambulatory persons with MS with slowed CPS using a highly-innovative and rigorous approach. If successful, the proposed study will provide the first Class I evidence for the efficacy of treadmill walking exercise training as a rehabilitative approach to improve CPS, its neural correlate, and possibly mitigate the impact of slowed CPS on functional outcomes in persons with MS who need such an intervention the most.

Specific Aim 1: Examine the efficacy of 3-months of progressive treadmill walking exercise training compared with a social contact, attention control condition (i.e., stretching-and-toning activities) on CPS and thalamocortical RSFC outcomes in fully-ambulatory persons with MS who have slowed CPS.

Hypothesis 1: Those who are randomly assigned to the treadmill walking exercise condition will demonstrate improvements in CPS and increased thalamocortical RSFC relative to those in the control condition.

Specific Aim 2: Examine thalamocortical RSFC as a potential mechanism of treadmill walking exercise training effects on CPS in fully-ambulatory persons with MS who have slowed CPS.

Hypothesis 2: Thalamocortical RSFC will mediate the effect of treadmill walking exercise training on CPS, such that increases in thalamocortical RSFC will explain exercise-related improvements in CPS.

Exploratory Aim 3: Examine the potential impact of 3-months of progressive treadmill walking exercise training on functional outcomes that are commonly associated with MS-related CPS impairment in fully-ambulatory persons with MS who have slowed CPS.

Exploratory Hypothesis 3: Those who are randomly assigned to the treadmill walking exercise training condition will demonstrate improvements in community participation, ability to perform activities of daily living, QOL, and functional mobility relative to those in the control condition.

3. Study Significance

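### Aim 2's rule for concluding mediation cannot establish direction or exclude a shared cause, because connectivity and SDMT changes span the same single interval

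*Combined protocol and SAP*

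**What the plan says.** Hypothesis 2 (protocol section 2) is directional: it predicts that "increases in thalamocortical RSFC will explain exercise-related improvements in CPS". The Statistical Design and Power part, under Specific Aim 2, turns this into a rule. Spearman correlations among group, SDMT change and RSFC change come first, as pre-conditions. Then: "In order to establish mediation, if the pre-conditions are met, group must influence change in SDMT in Step 1". In Step 2 the RSFC change must predict SDMT change, and the group coefficient must shrink and lose significance. Each of two RSFC measures is tested separately.

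On timing, the Abstract says: "All study outcomes will be administered before and after the 12-week study period by treatment-blinded assessors". No intermediate assessment is described. Within each assessment the SDMT is given at Visit 1 (section 5.2.3.1) and the MRI is done at Visit 2, two days later (section 5.2.3.3). Section 5.2.7 repeats this order at follow-up.

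On confounding, the SAP's Statistical Analysis paragraph adds covariates only if they differ between arms. The documents plan no reversed model, no set of mediator-outcome confounders and no sensitivity analysis for unmeasured ones.

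**The concern.** A mediation claim has a direction: exercise changes connectivity, and that change then speeds processing. Here RSFC and SDMT each supply one change score over the same 12 weeks, so no RSFC measurement precedes the SDMT change it is meant to explain. Randomisation protects the effects of group on RSFC and of group on SDMT. It does not protect the association between the two changes within arms, which is what Step 2 tests. The covariate rule concerns balance between arms, not common causes of the two changes.

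If the rule is applied as worded, a positive result would be reported as a neural mechanism. The same data could arise if faster processing altered connectivity, or if exercise moved both through something else, such as mood or fatigue.

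**Working it through.** **1. The plan's own figure.** Inputs from Sample Size Considerations: partial eta-squared 0.11, alpha 0.05, power 0.80, one covariate, two groups, 75% retention.
- f² = 0.11/0.89 = 0.1236, so f = 0.3516 and d = 2f = 0.703.
- Noncentral F with 1 and N−3 df and noncentrality N·f²: power is 0.797 at N=65 and 0.803 at N=66. The minimum is 66, as stated.
- 66/0.75 = 88, as stated.

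No sample-size figure is given for Aim 2.

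**2. Step 2 is symmetric.** The t statistic for the mediator is r·√(df/(1−r²)), where r is the partial correlation of RSFC change (M) and SDMT change (Y) given group, and df = N−3. Exchanging M and Y leaves r, and so t, unchanged.

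**3. Three causal models can imply the same data.** Let g be group (0 or 1), dM and dY the group effects in SD units, and ρ the within-arm correlation of the two changes.
- Forward: M = dM·g + e; Y = ρM + (dY − ρ·dM)g + √(1−ρ²)·e′.
- Reversed: Y = dY·g + e; M = ρY + (dM − ρ·dY)g + √(1−ρ²)·e′.
- Shared cause: M = dM·g + √ρ·u + √(1−ρ)·e; Y = dY·g + √ρ·u + √(1−ρ)·e′.

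All three give group effects dM and dY, unit within-arm variances and within-arm correlation ρ. No test computed from g, M and Y can separate them.

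**4. How often the full rule is met.** The rule was coded as three positive, significant Spearman correlations; Step 1 group p<.05; Step 2 mediator p<.05; and a group effect reduced to p>.05. dY = 0.703 is the planning value. The documents give neither ρ nor an RSFC effect size (only that the RSFC effects exceeded the SDMT effect), so ρ and dM are assumptions.

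| Setting | ρ | Forward | Reversed | Shared cause |
|---|---|---|---|---|
| N=66, dM=0.70 | 0.3 | 21% | 21% | 21% |
| N=66, dM=0.70 | 0.5 | 40% | 40% | 40% |
| N=66, dM=0.70 | 0.7 | 53% | 53% | 53% |
| N=66, dM=0.90 | 0.5 | 56% | 57% | 57% |
| N=88, dM=0.70 | 0.5 | 43% | 44% | 44% |

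Coding the rule without the Spearman pre-conditions gives up to about 23%, 43% and 56% in the first three rows. A joint-significance test of the indirect effect (group on M, and M on Y given group) at N=66, ρ=0.7 gives about 80% under all three models, so changing the test does not remove the ambiguity.

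**5. Where the match fails.** Suppose exercise reaches RSFC only through SDMT. The direct term in the reversed model is then zero and dM = ρ·dY, for example 0.5 × 0.703 = 0.35. The complete forward chain with the same SDMT effect has dM = dY/ρ, for example 0.703/0.5 = 1.41. At N=66:

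| ρ | Strictly reversed chain | Complete forward chain |
|---|---|---|
| 0.3 | 2% | 51% |
| 0.5 | 8% | 73% |
| 0.7 | 23% | 73% |
| 0.85 | 43% | 73% |

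**6. What the rule does reject.** With ρ = 0 (two unrelated exercise effects), it is met in about 0.5-0.8% of trials.

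**The case against.** The equal rates in step 4 are built in by matching the covariances, and the reversed model needs a direct exercise effect on RSFC to achieve that. Step 5 shows what happens without it: the rule does favour a complete forward chain over a strictly reversed one. That stands, and it limits the claim. It is partly offset because a strictly reversed chain without measurement error implies a smaller RSFC effect than SDMT effect, whereas the SAP reports the opposite order. The rivals that remain plausible are those in step 4.

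A reader might go further and infer that a positive Aim 2 is no evidence for the mechanism, or carries almost no information on direction. The documents and figures do not support that. The rule can fail, it almost always rejects unrelated effects, and it discriminates against a strictly reversed chain. Nor does the two-day gap show that RSFC changed after SDMT; it shows only that the design supplies no earlier RSFC measurement.

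A reader might also take Aim 2 for a confirmatory statement. Nothing in the documents calls it that. The step-down sequence covers Aim 1 outcomes, the aim itself speaks only of a possible mechanism, and the SAP describes the method as statistical mediation in a Phase I/II trial. That hedging is fair to the authors, but it does not reach the decision rule or Hypothesis 2.

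**Conclusion.** The concern holds in limited form. Meeting the Aim 2 rule shows that RSFC and SDMT changes are associated within arms, in a pattern consistent with mediation. It does not establish that RSFC drives SDMT, and it does not exclude a common cause. The symmetry of the Step 2 mediator test and the equivalence of the three models are algebraic and need no simulation.

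The pass rates rest on the planning effect d = 0.703 and on assumed values of ρ (0.3 to 0.85) and of the RSFC effect. Equality across models holds when the group effects and the correlation are matched. It does not extend to every reversed model: the strictly reversed chain passes in 2-43% of trials, against about 51-73% for the complete forward chain. The primary SDMT analysis is unaffected.

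**What to change.** - Under Specific Aim 2, replace the language of establishing mediation with a statement that a positive result is an association between RSFC change and SDMT change, consistent with mediation, which does not establish direction or exclude a common cause. Reword Hypothesis 2 to match.
- Report the reversed model (SDMT change as mediator of RSFC change) beside the planned one. It displays the ambiguity and cannot resolve it.
- Pre-specify a sensitivity analysis for unmeasured mediator-outcome confounding: for example, how large a residual RSFC-SDMT correlation from shared causes would remove the indirect effect.
- Do not adjust for change in VO2peak. It is the trial's manipulation check and may lie on the causal path. In a simulated true chain from exercise through VO2peak and RSFC to SDMT (assumed VO2peak effect 0.8-1.0 SD, paths 0.7-0.99), adjustment cut the pass rate from 44-75% to 0-1%, which would look like refutation of a true mechanism.

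The cost is some rewording and a few regressions on data already planned, with no added participants or visits. The downside is a more modest mechanistic claim.
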